8.3 Follow up visits (Visits 2-5)

Four follow up visits will be conducted and 1 week, 1Month, 3 Months and 6 months post last treatment.

The follow up visits will include the following assessments:

- Camera photos
- Cellulite evaluation
- AE evaluation recording
- Concomitant medication recording

9. Efficacy and Safety Evaluations

9.1 Efficacy Measures

The below assessments will be conducted at baseline and follow-up visits.

Photos from all time points (baseline before treatment and at follow-up visits) will be evaluated by the treating physician and 2 blinded independent evaluators.

[figure not shown]
Evaluation goals are rating the degree of cellulite.

9.2 Safety Measures

Observation, assessment and recording of adverse events. Evaluations will be done immediately after treatment and at all follow-up visits, to determine if adverse events develop or persist. The frequency, severity and causality of all adverse events will be recorded.

Possible CelluTite adverse effects include but are not limited by:

- Discomfort or pain
- Excessive skin redness (erythema)
- Excessive skin swelling (edema)
- Ecchymosis
- Damage to natural skin texture (crust, blister, burn)
- Change of pigmentation (hyper- and hypo-pigmentation)
- Scarring

- Very slight risk of infection
- Incision port scarring
- Surface Irregularity
- Numbness
- Seroma
- Side effects related to anesthesia

Possible Morpheus8 adverse effects include but are not limited by:

- Discomfort or pain
- Excessive skin redness (erythema)
- Excessive skin swelling (edema)
- Damage to natural skin texture (crust, blister, burn)
- Change of pigmentation (hyper- and hypo-pigmentation)
- Localized infection
- Scarring

Erythema lasting not longer than 24h and edema for 1-3 weeks is a typical skin reaction to the Morpheus8 treatment.

Crusting from the ablated dots will exfoliate naturally after 1-3 weeks.

Adverse events will be classified as Mild, Moderate, and Severe.

The duration of the adverse event until it subsides will also be recorded.

10. Subject Compliance

10.1 Subject Discontinuation or Withdrawal

Subjects will be suspended temporarily or terminated from the study whenever considered necessary for their welfare.

[figure not shown]
The investigator may withdraw a subject if, in his judgment, it is in the best interest of the subject, if the subject cannot comply with the protocol, or if a Serious Adverse Event occurred.

Each subject must complete the 6 months follow-up visit in order to remain in the study.

If a subject withdraws, the reason must be recorded in the CRF Exit Form and signed by the Investigator.

10.2 Compensation for Study Participation

There is no cost to subject for participation and any potential stipend will be clearly explained in the ICF.

11. Risk / Benefit Analysis

11.1 Potential Risks

Risk is the product of the likelihood that an adverse medical event will occur times the severity of the event. The main potential risks of using the CelluTite an Morpheus8 handpieces are specified below.

Possible CelluTite adverse effects include but are not limited by:

- Discomfort or pain
- Excessive skin redness (erythema)
- Excessive skin swelling (edema)
- Ecchymosis
- Damage to natural skin texture (crust, blister, burn)
- Change of pigmentation (hyper- and hypo-pigmentation)
- Scarring
- Very slight risk of infection
- Incision port scarring
- Side effects related to anesthesia
- Surface Irregularity
- Numbness
- Seroma

Possible Morpheus8 adverse effects include but are not limited by:

[figure not shown]
- Discomfort or pain
- Excessive skin redness (erythema)
- Excessive skin swelling (edema)
- Damage to natural skin texture (crust, blister, burn)
- Change of pigmentation (hyper- and hypo-pigmentation)
- Localized infection
- Scarring

Erythema lasting not longer than 24h and edema for 1-3 weeks is a typical skin reaction to the Morpheus8 treatment.

Crusting from the ablated dots will exfoliate naturally after 1-3 weeks.

11.2 Benefits

Subjects may experience cellulite improvement. Each individual may get different level of clinical aesthetic results.

12. Adverse Events Reporting

12.1 Definitions

Adverse Event:

An Adverse Event (AE) is any untoward medical occurrence (sign, symptom, illness, abnormal laboratory value, or other medical event) in a subject. This definition does not imply that there is a relationship between the adverse event and the device. (Significant device failure may constitute an adverse event if an undesirable experience occurs).

An Adverse Device Effect (ADE) is any untoward and unanticipated response to a medical device. This definition includes any event resulting from insufficiencies or inadequacies in the instructions for use or the deployment of the device, or any event that is a result of a user error.

Serious Adverse Event (SAE):

A serious adverse event (SAE) is any adverse event that:

- Led to death
- Led to a serious deterioration in the health of the subject that resulted in a lifethreatening illness or injury
- Resulted in a permanent impairment of a body structure or a body function
- Required in-subject hospitalization or prolongation of existing hospitalization
- Resulted in medical or surgical intervention to prevent permanent impairment to body structure or a body function
- Led to fatal distress, a congenital abnormality, birth defect or death

Unanticipated Adverse Event:

An unanticipated adverse event is any serious, device-related adverse event, if that event was not previously identified in the risk analysis and Informed Consent form in nature, severity, or frequency.

AE Severity:

[figure not shown]
Adverse events are graded according to severity as follows:

Mild	Sign or symptom, usually transient, requiring no special treatment and	
	generally not interfering with usual activities.	
Moderate	Sign or symptom, which may be ameliorated by simple therapeutic	
	measures; yet, may interfere with usual activity.	
Severe	Sign or symptom that are intense or debilitating and that interfere w	
	usual activities. Recovery is usually aided by therapeutic measures.	

Relationship to Device:

The relationship of the adverse event to the treatments or procedures is defined as follows:

Most Probably Related	Follows a reasonable temporal sequence from study device
iviost Frobably Related	delivery/retrieval and cannot be reasonably explained by known

	characteristics of the subject's clinical data or the surgical procedure applied.		
	Follows a reasonable temporal sequence from study device		
Possibly Related:	delivery/retrieval but could have been produced by the subject's clinical state or by the surgical procedures regardless of the study device.		
Probably not Related:	Temporal association is such that the study device is not likely to		
Trobubly flot Nelated.	have had any reasonable association with the observed event.		
Unrelated	No relationship to study device activation is perceived		

12.2 Anticipated Adverse Events in this Clinical Evaluation

Possible CelluTite adverse effects include but are not limited by:

[figure not shown]
- Discomfort or pain
- Excessive skin redness (erythema)
- Excessive skin swelling (edema)
- Ecchymosis
- Damage to natural skin texture (crust, blister, burn)
- Change of pigmentation (hyper- and hypo-pigmentation)
- Scarring
- Very slight risk of infection
- Incision port scarring
- Side effects related to anesthesia
- Surface Irregularity
- Numbness
- Seroma

Possible Morpheus8 adverse effects include but are not limited by:

- Discomfort or pain
- Excessive skin redness (erythema)
- Excessive skin swelling (edema)
- Damage to natural skin texture (crust, blister, burn)
- Change of pigmentation (hyper- and hypo-pigmentation)
- Localized infection
- Scarring

Erythema lasting not longer than 24h and edema for 1-3 weeks is a typical skin reaction to the Morpheus8 treatment.

Crusting from the ablated dots will exfoliate naturally after 1-3 weeks.

12.3 Precautions to Minimize Complications

A list of warning and precautions is provided in the Operator Manual which is provided to site personnel.

Additionally, the exclusion criteria listed in this protocol further reduce the abovementioned risks.

12.4 Investigator Records

The Investigator will report all Adverse Events which occur with each subject throughout the study and follow-up period and will record them in the CRF Adverse Events Investigation Form. The Investigator will categorize Adverse Events according to:

- Serious or non-serious
- Severity
- Anticipated or unanticipated
- Relationship to device use

12.5 Investigator Reporting of AEs

The Investigator will report all serious adverse events (SAEs) to InMode MD Ltd by telephone as soon as becoming aware of them. A written follow-up report will be emailed or faxed to InMode MD Ltd and the reviewing IRB within 24 hours and will include the following information:

[figure not shown]
- 1. Nature of AE
- 2. Statement regarding the degree to which it is considered device related, and rationale.
- 3. Results of any diagnostic tests that were performed.
- 4. Description of any treatment implemented.
- 5. Statement of subject's current clinical status.
- 6. Investigator's signature and date.

Non-serious adverse events that are unanticipated and may be device related will be reported to the InMode MD Ltd by telephone within 24 hours. A written follow-up written report will be emailed or faxed to InMode MD Ltd within 5 working days and will include the following information:

- 1. Nature of adverse effect.
- 2. Statement as to why it is considered unanticipated.
- 3. Statement as to the degree to which it is considered device related, and rationale.
- 4. Results of any diagnostic tests that were performed.
- 5. Description of any treatment implemented.
- 6. Statement of subject's current clinical status.
- 7. Investigator's signature and date.

All other Adverse Events will be reported in writing to InMode MD Ltd in writing within 5 working days of the Investigator becoming aware of them.

The Investigator will continue to clinically monitor the AE, with laboratory tests where appropriate, until it is resolved, stabilized or there is a return to baseline.

Clinical Evaluation of Safety and Efficacy of The Celluttie Treatment			
Protocol No:	DO608110C	Rev. Date: August 15, 2019	
IRB ID:	7030		

13. Regulatory Aspects

13.1 Institutional Review Board

The study protocol, informed Consent forms (all versions), and any specific advertising will be submitted to and approved by Sterling Institutional Review Board (IRB), at [name], Toll-Free: [contact], [contact], [contact] before the start of the study. A form must be signed by the chairman or designee of the IRB noting the approvals. This notification will be provided to the sponsor.

13.2 Protocol

[figure not shown]
Protocols will be noted as approved by the Investigator by placement of his signature on the Investigator's Signature Page. The protocol and Informed Consents will be provided, and the site shall assure IRB approval prior to any study related activities.

13.3 Informed Consent

An Informed Consent that includes all of the relevant elements currently required by FDA or state regulations will be provided to each prospective study patient at screening and before enrolling into the study. The type and method of study, any potential or possible hazards, and the patient's right to withdraw from the study at any time will be explained to the patients by the Investigator of designee. Once the Investigator is assured that an individual candidate understands the implications of participating in this study, the patient will be asked to give Consent by signing and dating in the appropriate areas of the Informed Consent form. The Investigator or Designee will also sign and date the form. A copy of the IRB approved IC form will also be provided to InMode MD Ltd.

13.4 Protocol and Informed Consent Changes

Changes to the protocol or Informed Consent Form will be implemented as amendments to the original document and approved by the IRB. The approvals will be processed in accordance with the established IRB procedures. Copies of all protocol and IC amendments/revisions, along with letters noting IRB approval, will be submitted to InMode MD Ltd, as this may affect safety. Any addenda, amendment or revision that substantially alters the study design or increases potential risk to the patient requires the patient's Consent to continue in the study.

13.5 Product Accountability

All device and related materials receipt, inventory, dispensing, and reconciliation records will be maintained in compliance with Federal Regulations. Upon completion or termination of the study the site will be responsible for retaining all partial and unused products under FDA regulations.

13.6 Privacy of Personal Data

The subject's name and personal data will remain confidential and will not be published in any way. All reports and communications relating to study subjects will identify the subject only by his/her case number and study 3-letter code. The Study staff will complete subject identification in a confidential enrolment log, which will be used for the purposes of traceability and follow-up. This will be treated with strict adherence to professional standards of confidentiality and will be filed under adequate security and restricted accessibility

14. Documentation

[figure not shown]
14.1 Documentation List

Accurate, complete and timely documentation is essential to the successful conduct of this study. The following documents will be created and maintained:

- 1. Informed Consent Forms (ICFs).
- 2. Case Report Forms (CRFs).
- 3. Adverse effect reports to sponsor.
- 4. Adverse effect reports to IRB.
- 5. Inventory Log.
- 6. Monitoring logs.
- 7. IRB approval for protocol.
- 8. IRB approval for informed Consent.
- 9. Final report to Sponsor and IRB.
- 10. Records of protocol deviations.
- 11. Record of protocol amendments.
- 12. 1 copy of each protocol revisions.
- 13. 1 copy of each CRF revision.
- 14. Clinical Trial Agreement.
- 15. All correspondence relating to study.

14.2 Case Report Forms (CRFs)

CRFs will be designed for recording the required demographic and clinical information and the variables to be analysed, as described by this protocol.

CRFs will be completed by the authorized Investigator or a designee who will be properly trained on study procedures and data recording requirements. Upon completion, the CRFs will be signed by the Principal Investigator.

CRFs will be provided by the sponsor, one CRF per subject, each one numbered.

Study data will be recorded directly onto the CRF as soon as it is collected. The following data will be recorded pre-procedure, during the procedure, and post-procedure on the CRFs:

- 1. Baseline Data Form to be used for screening subjects for inclusion in the study and to record subject's demographic data and medical history.
- 2. Training Form to be used for recording relevant training information.
- 3. Treatment Visit Forms to be used to record procedural details, procedural complications, technical performance of the device, test results and other relevant information related to the procedure and device.
- 4. Unscheduled Visit Form to be used to record procedural details, procedural complications, technical performance of the device, and other relevant information related to the procedure and device during an unscheduled visit to site.
- 5. Termination Form to be used to record all details regarding the termination of the subject, whether a result of study completion or premature withdrawal.
- 6. Exit Form To be completed after all study procedures, follow-up and completion of AE investigation for the subject.
- 7. Adverse Event Investigation Form to be used to report all AE, if occurred.

14.3 Protocol Modifications

An amendment to the protocol may be proposed by an Investigator or the Sponsor. The amendment will be prepared and approved by the Sponsor according to the Sponsor's Procedure. Significant amendment will be submitted to the IRB for approval before implementation.

If for any unexpected reason it is necessary to deviate from the procedures stated above, the protocol deviation should be discussed with the Sponsor representative. It must be approved by the Investigator and Sponsor representative. The deviation and reasons for it will be described in the appropriate Protocol Deviation Form, signed and filed in the relevant section of the Sponsor Study File following approval.

A copy of the document must be filed in the Investigator Study File.

Any deviation must be noted in the Study Report. If a deviation has any implication of impact on the study objectives it must also be included in the summary.

14.4 Maintenance and Retention of Records

Investigators will maintain all study related documentation for a period of two years following: 1) marketing authorization for device commercialization, or 2) sponsor's withdrawal of submission for approval, or 3) completion of the study.

Clinical Evaluation of Safety and Efficacy of The CelluTite Treatment			y of The CelluTite Treatment
	Protocol No:	DO608110C	Rev. Date: August 15, 2019
	IRB ID:	7030	

All printouts and records of tests and procedures are to be kept in a secure and safe place throughout the study. Once the study is completed, the records will be kept as required by local regulations, but in no case less than the period defined above.

The Investigator will not relocate or dispose of any study documents before obtaining sponsor's written permission.

Documentation should be kept so as to make its retrieval easy should an audit take place.

All study documentation will be kept locked under the Investigator's responsibility.

14.5 Reports

Study reports include a Final Report that will be issued by the Sponsor. Report format will be designed by the Sponsor.

All study reports will be signed by the Principal Investigators approving its contents, analysis, results and conclusions.

AE related reporting requirements are specified above.

15. Monitoring Plan

15.1 General Considerations

Monitoring functions will be performed in compliance with Good Clinical Practices, EN ISO 14155, and as outlined in 21CRF§812.43(d) and 21CRF§812.46. InMode MD Ltd procedures detail monitoring procedures and monitor responsibilities.

The study will be monitored periodically, per Sponsor discretion and site monitoring plan, for the purposes of: a) verifying compliance to the protocol and applicable regulations, and b) verifying correspondence of CRF data to original entries in source files.

[figure not shown]
15.2 On-Site Visits

Periodic on-site monitoring visits are intended to assess the Investigator's adherence to the protocol, maintenance of records and reports, and review of source documents for accuracy, completeness, and legibility, and monitoring of Adverse Events.

During periodic visits the monitor is required to:

- Assess the progress of the study towards meeting study objectives.
- Identify any concerns that stem from observations of device performance and/or review of the subject's CRF, study management documents, and informed Consent documents.
- Monitor AE reporting and investigations.

Reports of on-site visits will be submitted by the monitor and will include, as applicable, resolution of concerns, completion of appropriate follow-up activities, completion of assigned tasks, and corrective actions. Visits may be performed using a video conference or phone call and will not be actual physical visits.

15.3 Site Initiation Meeting

A Site Initiation visit will take place prior to initiation of study procedures. All study related documents and procedures will be explained to all staff involved in the study to ensure understanding of the study requirements.

15.4 Adverse Event Reporting and Follow-up

Monitoring of adverse events, their follow up and outcomes will take place at each study visit.

15.5 Site Closure Visit

Upon approval of the Final Report, a Site Closure Visit will be conducted to ensure that all used and unused devices have been returned to the Sponsor, all relevant documentation is filed and archived under the Investigator's responsibility according to regulations.

16. Data analysis.

16.1 Analysis Sets

[figure not shown]
- Safety Analysis Set
 - The safety analysis set will include all subjects using treatment procedures at least a single time.
- Performance Analysis Set
 - Performance analysis set will consist of all subjects providing at least one post treatment performance measurement.
- Treatment of Missing Values
 - Only observed data will be used; i.e. missing data will not be imputed.

16.2 Statistical Analysis

[figure not shown]
Means, and standard deviations for each characteristic will be calculated. Paired sample t-test will be computed to assess changes in before treatment and follow-up scores. Statistical significance will be calculated and two-tail significance level of 0.05 will be used. All analyses will be conducted using IBM SPSS 21.0.

17. References

[figure not shown]

- 2. Mulholland RS. Nonexcisional, minimally invasive rejuvenation of the neck. Clin Plast Surg. 2014;41:11–31.
- 8. [name]; [name]; [name]; [name], FACS; [name], FACS; and A. [name] A Multicenter Study for Cellulite Treatment Using a 1440-nm Nd:YAGWavelength Laser with Side-Firing Fiber. Aesthetic Surgery Journal 2016, Vol 36(3) 335–343

18. Investigator Study Acknowledgment

Investigator's Statement:			
I have read and understand the foregoing protein entitled: "Clinical Evaluation of Safety and Efficiency No.: DO608110C, and agree to conduct the Study	icacy of The CelluTite Treatment.", Study		
Investigator's Name (Please print)	Investigator's Title		
Investigator's Signature	Date		

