Cover Letter:

Enclosed bellow documents are part of the Clinical Trial NCT03769649

Study Name: Clinical Evaluation of Safety and

Efficacy of The CelluTite Treatment

Revision Date: August 15, 2019

Clinical Evaluation of Safety an	l Efficacy of The C	ElluTite Treatment
----------------------------------	---------------------	--------------------

IRB ID: 7030

Rev. Date: August 15, 2019

Study Name: Clinical Evaluation of Safety and Efficacy of The

CelluTite Treatment

Protocol No.: DO608110

Revision No.: 4

Sponsor: InMode MD Ltd.

[name]

[name]

[name]

[name]

[contact]

[contact]

	Clinical Evaluation	on of Safety and Efficac	y of The CelluTite Treatment
	Protocol No:	DO608110C	Rev. Date: August 15, 2019
•	IRB ID:	7030	

Clinical Evaluation of	Safety	and Efficacy o	of The Cell	ˈuTite Treatment

IRB ID: 7030

Rev. Date: August 15, 2019

1. Protocol Synopsis

Study Title	Evaluation of Safety and Efficacy of The CelluTite Treatment
Protocol No	DO608110C
Sponsor	InMode MD Ltd.
Device	InMode RF system CelluTite RFAL hand piece HP172248.
	Morpheus8 Applicator
Study Design	Prospective single centre, open label clinical study.
Study Objectives	The aim of the study is to evaluate the safety and efficacy of cellulite treatment with HP172248 and Morpheus8.
Study Sites	[name], [name]
Patient Population and Sample Size	Approximately 10 female subjects , aged 18-70 having grade II and mild/moderate grade III cellulites.
Treatment areas	Exterior (lateral) and posterior thighs
	Optional: Buttocks with Morpheus Applicator only
Study Duration	Study duration for each subject is approximately seven months (including screening, one treatment and four follow-up visits at 1 week, 1 month, 3 months and 6 months post treatment.
	Overall study duration will be approximately 12 months, depending on the subject recruitment rate.
Efficacy Endpoints	Photographs evaluation: Photos from all time points (baseline and follow-up visits) will be evaluated by the treating physician and 2 blinded independent evaluators.
	Optional: Photos will be taken using QuantifiCare (imaging specializing in skin evaluations in clinical trials) at baseline and 6M FU visit.
	Evaluation goals are rating the degree of cellulite according to Clinician Reported Photonumeric Cellulite Severity Scale (CR-PCSS).

Clinical Evalua	tion of Safety and Eff	icacy of The CelluTite Treatment	

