6.2 Safety Endpoint

Observation, assessment and recording of adverse events. Evaluations will be done immediately after treatment and at all follow-up visits. The frequency, severity and causality of all adverse events will be recorded.

Possible CelluTite adverse effects include but are not limited by:

- Discomfort or pain
- Excessive skin redness (erythema)

- Excessive skin swelling (edema)
- Ecchymosis
- Damage to natural skin texture (crust, blister, burn)
- Change of pigmentation (hyper- and hypo-pigmentation)
- Scarring
- Very slight risk of infection
- Incision port scarring
- Surface Irregularity
- Numbness
- Seroma
- Side effects related to anesthesia

Possible Morpheus8 adverse effects include but are not limited by:

- Discomfort or pain
- Excessive skin redness (erythema)
- Excessive skin swelling (edema)
- Damage to natural skin texture (crust, blister, burn)
- Change of pigmentation (hyper- and hypo-pigmentation)
- Localized infection
- Scarring

Erythema lasting not longer than 24h and edema for 1-3 weeks is a typical skin reaction to the Morpheus8 treatment.

Crusting from the ablated dots will exfoliate naturally after 1-3 weeks.

Adverse events will be classified as Mild, Moderate, and Severe. The duration of the adverse event until it subsides will also be recorded.

7. Study Population

[figure not shown]

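### Section 16.2 names no primary visit, rater or score for its paired t-tests at 0.05 (3 to 18 tests on the section 8 visits), and nothing ranks the blinded evaluators above the treating physician

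*Combined protocol and SAP*

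**What the plan says.** Section 16.2 is the whole of the planned inference. It opens with "Means, and standard deviations for each characteristic will be calculated", continues with "Paired sample t-test will be computed to assess changes in before treatment and follow-up scores", adds that a "two-tail significance level of 0.05 will be used", and names the software. It does not say which follow-up visit, whose rating or which score enters the test, and it has no adjustment or ordering rule.

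The other sections supply the pieces but do not rank them:

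- **Visits.** Section 8 bases efficacy on 1, 3 and 6 months against baseline and puts none of them first. Section 8.3 also schedules week 1 ("Four follow up visits will be conducted and 1 week, 1Month, 3 Months and 6 months post last treatment") and lists "Cellulite evaluation" among the assessments at every follow-up.
- **Scores.** Section 6.1 describes CR-PCSS as two features, dimple count and linear undulations, each graded 0 to 4. It defines no total and no lead feature.
- **Raters.** The synopsis and section 9.1 list the treating physician and two blinded independent evaluators side by side. No section says how three ratings become one, or which prevails if they disagree.
- **Missing data.** Section 16.1 uses observed data only. Its performance set needs just one post-treatment measurement.

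**The concern.** When several tests could each be read as the efficacy result, 0.05 is the error rate of each test and not of the conclusion. The study has a single arm, and these before/after comparisons are its only planned efficacy inference, so no other analysis would correct a chance finding.

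The missing rater rule matters separately. The study is open label, and only two of the three raters are called blinded, so the treating physician is best read as unblinded. As written, a significant change in that physician's own ratings has the same standing as one in the blinded evaluators' ratings. A multiplicity adjustment would control chance but would not remove bias from an unblinded rater's scores. The size of any such bias cannot be derived from the documents.

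**Working it through.** **Stated figure.** The only statistical design figure in the plan is the two-sided 0.05. It is an input, so there is nothing to reproduce beyond a check that one test gives 5%. Simulation of a single test at n=70 gave 0.050.

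**Number of tests.** Count = visits × raters × scores, with one score per subject. The inputs are 3 visits (section 8), 1 combined rating or 3 raters (section 9.1), and 1 grade or 2 features (section 6.1).

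- One grade, one rating: 3 × 1 × 1 = 3
- Two features, one rating: 3 × 1 × 2 = 6
- One grade, three raters: 3 × 3 × 1 = 9
- Two features, three raters: 3 × 3 × 2 = 18

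The plan does not say whether lateral and posterior thighs are scored separately. If they were, these counts would double.

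**Chance of at least one p<0.05 with no true change.** For independent tests it is 1 − 0.95^k:

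- k=3: 1 − 0.95^3 = 0.143
- k=18: 1 − 0.95^18 = 0.603

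Independence is not expected, because the same women are rated repeatedly. Changes were therefore simulated as normal with a common correlation rho and tested by one-sample t-test on the change (n=70, 20,000 runs, two-sided):

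| Tests | rho 0.5 | rho 0.7 | rho 0.9 |
|---|---|---|---|
| 3 | 0.125 | 0.110 | 0.084 |
| 6 | 0.209 | 0.170 | 0.111 |
| 9 | 0.277 | 0.208 | 0.124 |
| 18 | 0.401 | 0.276 | 0.150 |

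Counting only significant improvements, against a nominal 2.5%, the risk is 4-6% for 3 tests and 8-20% for 18. At n=10, the synopsis figure, the two-sided ranges are 9-13% for 3 tests and 17-43% for 18, so the conflict between 10 and 70 subjects barely alters the picture.

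**Why the range is not a bound.** Within one rater and feature, with equal variances and equal between-visit correlation p, two changes from the same baseline correlate (1 − p)/(2 − 2p) = 0.5. Across raters or features that argument fails, because each rater gives a separate baseline score. Keeping 0.5 between visits and multiplying it by a correlation of 0.5, 0.25 or 0 for differing raters and the same again for differing features gives about 47%, 53% and 55% for 18 tests (n=70). All three lie above the 15-40% in the table.

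**Limits.** The documents give no correlations, so every percentage is illustrative. Normal changes were simulated although the scores are ordinal 0 to 4, which matters most at n=10.

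**The case against.** The strongest reply is that the harm depends on a rule the plan does not contain. The stated objective is to evaluate safety and efficacy; there is no hypothesis, success criterion or decision rule. An inflated error rate follows only if results are used selectively. That stands, and it makes the size conditional. It does not close the gap: the plan sets a significance level, never calls its tests exploratory, and leaves selective use open.

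A second reply is that section 8 refers to a cellulite grade, and section 9.1 to a degree of cellulite, both in the singular, so one score per visit may be meant. That is the 3-test case. It remains possible, and its risk is still above 5%.

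A third is that 6 months is implicitly primary. Section 10.1 says "Each subject must complete the 6 months follow-up visit in order to remain in the study", and the optional imaging is tied to the same visit: "Photos will be taken using QuantifiCare (imaging specializing in skin evaluations in clinical trials) at baseline and 6M FU visit". These passages favour choosing 6 months, but one is a retention rule and the other an optional procedure. Neither makes that visit primary.

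A reader might also infer stronger claims that the documents do not support:

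- **24 tests.** Week 1 is photographed and rated, and 4 × 3 × 2 = 24. But section 8 limits the efficacy comparison to 1, 3 and 6 months, the synopsis calls week 1 a safety follow-up, and rating a visit is not testing it.
- **No blinded assessment.** The blinded evaluators are in the plan. What is missing is their priority.
- **A 60% false-positive rate.** That figure needs 18 independent tests, which repeated ratings of the same women would not be.

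**Conclusion.** The point holds as a pre-specification gap that should be fixed. On the section 8 visits the plan leaves 3 to 18 tests of equal standing, with no rule for whose ratings count. If one significant result is enough for an efficacy claim, the risk under no true change is about 8-13% for 3 tests and 15-40% for 18, at n=70 and assumed common correlations of 0.9 to 0.5. With weaker agreement across raters or features, 18 tests gave roughly 47-55%. The conclusion that the risk exceeds 5% holds in every case examined, but its size rests on correlations the documents do not give and on a success rule they do not state. That the treating physician is unblinded is an inference from the open-label design and from which raters are called blinded.

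**What to change.** Before any scores are seen, name one primary comparison in section 16.2. One example is the change from baseline to 6 months in one defined CR-PCSS score (a single feature or a stated combination), averaged over the two blinded evaluators to one value per subject, tested at two-sided 0.05. With one test, the stated 0.05 is again the error rate of the claim.

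Report the treating physician's ratings, the other feature and the 1- and 3-month visits as supportive, either as estimates with confidence intervals or with Holm adjustment. Keep week 1 out of the efficacy tests, consistent with section 8.

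If no confirmatory test is intended, label all tests exploratory and still lead with the blinded evaluators' mean.

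**Cost.** This is a wording change, with no new visits or data. There are two downsides. The physician's scores and the 1- and 3-month visits can no longer carry the efficacy claim. And because section 16.1 uses observed data only, a 6-month primary rests on the women who have a 6-month score, so the number missing and the results at 1 and 3 months should be reported beside it.

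Three related matters are side points and not part of this claim: the word blinded is absent from section 6.1, the plan does not describe coding and shuffling of photos, and the optional buttocks area could be reported separately.
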